7.2. Rationale

Avapritinib is approved in the US for the treatment of adults with unresectable or metastatic GIST harbouring a PDGFRA exon 18 mutation, including PDGFRA D842V mutations. On 24 September 2020, the European Commission granted a CMA for avapritinib as monotherapy for GIST harbouring the PDGFRA D842V mutation. The approval status of avapritinib in different regions and indications is provided in Annex 4.

To address the Specific Obligation of the CMA in Europe and to provide further evidence of the positive benefit-risk profile of first-line treatment with avapritinib in patients with metastatic and unresectable GIST harbouring mutations in PDGFRA D842V, this non-interventional post-authorisation safety study (PASS) aims to collect long-term safety and efficacy data in the first-line population. Data from at least 50 patients with PDGFRA D842V-mutated GIST who receive avapritinib in the first-line or following \leq 4 months of imatinib treatment will be evaluated from sites worldwide. Real-world biomarker testing practices and treatment landscape for metastatic or unresectable GIST patients suggest a significant percentage of patients do not receive complete biomarker testing for KIT and PDGFRA prior to first-line treatment initiation. Given this, the inclusion criteria of this study also allows for enrolment of patients with PDGFRA D842V-mutated GIST who were treated with standard of care imatinib for \leq 4 months prior to initiation of avapritinib. Patients will be evaluated for AEs and efficacy outcomes (i.e. survival and tumour response). This data will provide important information on the safety and efficacy of avapritinib in this ultra-rare patient population.

8. **RESEARCH QUESTION AND OBJECTIVES**

The overall objective is to collect long-term safety and efficacy data for avapritinib in first-line patients with PDGFRA D842V-mutated GIST.

8.1. **Primary Objective**

To describe types, severity and rates of AEs, SAEs, AEs leading to discontinuation or decreased dosing of avapritinib, AESIs, and deaths.

This PASS has been implemented following a commitment to the EMA to address the Specific Obligation of the CMA in Europe to provide additional safety data for patients with PDGFRA D842V-mutated GIST on first-line avapritinib treatment.

8.2. Secondary Objectives

To evaluate efficacy in terms of disease response to treatment, PFS and OS as well as duration of treatment and duration of response.

9. **RESEARCH METHODS**

9.1. Study design

This is a multinational, open-label, observational PASS that will evaluate the long-term safety and efficacy of avapritinib in the first line or following ≤ 4 months of imatinib treatment in at least 50 patients with PDGFRA D842V-mutated GIST. Three patient populations are planned to be enrolled:

- Patients with PDGFRA D842V-mutated GIST who are scheduled to receive avapritinib in the first-line (or have received imatinib for ≤4 months)
- Patients with PDGFRA D842V-mutated GIST who are already receiving treatment with avapritinib (in the first-line or following ≤ 4 months of imatinib treatment)
- Patients with PDGFRA D842V-mutated GIST who previously received treatment with avapritinib in the first line or following ≤4 months of imatinib treatment and have discontinued treatment

In addition to evaluating safety and efficacy of first-line avapritinib treatment, patients who were initially treated with imatinib for \leq 4 months are also being in included this study to allow for practical, real-world, clinical experience with use of avapritinib in the PDGFRA D842V-mutated GIST population setting and increase the feasibility of study completion in this ultra-rare patient population.

Informed consent will be obtained from all patients according to the regulatory and legal country-specific requirements of the participating site before enrolment in this study.

Patients who were scheduled to receive avapritinib prior to enrolment will initiate treatment after enrolment in this study based on the locally approved product label prescribing information. If a patient was already receiving avapritinib prior to enrolment, they will continue treatment at the same dose after enrolment. The dose level may be adjusted based on the locally approved product label prescribing information. Investigators must refer to the local prescribing information for contraindications, warnings and precautions as well as use in specific populations. As this study is observational, the decision to treat patients with avapritinib will be independent from the decision to enrol patients into the study.

Baseline and follow-up assessments will be in accordance with local standard medical care. Both prospective and retrospective data collection will be performed in this study. All patients who will initiate or continue treatment with avapritinib after enrolment will have prospective data collection for 24 months on the study. For patients who have received avapritinib prior to enrolment in this study, retrospective data may also be collected (if data are available). Retrospective data collection will be performed at the participating investigator site through extraction of available data from the patient's medical records. The data collection plan is provided in Table 1.

9.2. Setting

9.2.1. Inclusion criteria

A patient who meets all of the following criteria is eligible for inclusion:

- Written informed consent.
- Male or female, ≥ 18 years of age at the start of avapritinib treatment
- Histologically or cytologically-confirmed diagnosis of unresectable or metastatic GIST harbouring the D842V mutation in the PDGFRA gene
- Is scheduled to receive, previously received, or currently receiving first-line treatment with avapritinib consistent with the approved labelling for unresectable or metastatic GIST. Note: Patients who were treated with imatinib for ≤4 months prior to initiation of avapritinib treatment are also eligible.
- For patients who received avapritinib treatment and discontinued prior to enrolment in this study, their retrospective data must be available
- No concomitant treatment with other anticancer therapy

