Cognitive effects occurred in 182 (33%) of the 550 patients with GIST who received avapritinib at starting doses of either 300 or 400 mg once daily. Most cognitive effects were Grade 1 (89%), with Grade \geq 2 occurring in 11% of 550 patients. Memory impairment occurred in 20% of patients, <1% of these events were Grade 3. Cognitive disorder occurred in 12% of patients; <1% of these events were Grade 3. Confusional state occurred in 5% of patients; <1% of these events were Grade 3. Confusional state occurred in 5% of patients; <1% of these events were Grade 3. Encephalopathy occurred in <1% of patients; <1% of these events were Grade 3. SAEs of cognitive effects were reported for 7 of the 550 (1.3%) patients. Overall, 1.3% of patients required permanent discontinuation of avapritinib for a cognitive effect. Cognitive effects were reported by 46% of the patients in BLU-285-1101, most cases were mild-moderate AEs (90% Grade 1-2 AEs, 10% Grade 3 AEs). Consistent with the overall trend of a slightly less severe safety profile observed in the Phase III trial, cognitive effects were reported by 26% of the patients in BLU-285-1303, 95% Grade 1-2 AEs and 5% Grade 3 AEs. The early recognition and management of cognitive effects might explain the lower incidence in the Phase III trial as

AESIs of cognitive effects were higher in the 400 mg starting dose group compared to the 300 mg group in BLU-285-1101 (48% vs 39%). However, the median treatment duration for patients receiving avapritinib (any dose) in the Phase III trial was also considerably shorter (8.9 months) than in the Phase I trial (23.2 months). No fatal cognitive events were reported in either study. In the clinical development program, the probability of experiencing a cognitive effect increased over the first 7 to 8 months of treatment and then reached a plateau. Non-clinical mechanistic studies could not clearly identify the underlying mechanism for cognitive effects (i.e., memory impairment). Clinical factors associated with an increased likelihood of experiencing Grade \geq 2 cognitive effects include a medical history of cognitive effects, prior regorafenib use and age \geq 65 years. Brain imaging studies of patients experiencing cognitive effects effect symptoms during the clinical studies did not reveal any associated anatomical changes.

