9.4. Data Sources

For patients who initiate or continue to receive avapritinib in this study, data will be collected prospectively for 24 months following enrolment. For patients who have already received avapritinib prior to enrolment, retrospective data will also be collected (if available). Retrospective data collection will be performed at the participating investigator site through extraction of available data from the patient's medical records as per local law and regulations. Data will include: relevant baseline data at the time of the first dose of avapritinib and safety data from the time of the first dose of avapritinib to the end of follow-up, i.e. at least 24 months, until study discontinuation for any reason, or 30 days after the last dose of avapritinib; whichever comes first. In addition, data will include efficacy data (i.e. treatment response) between the first dose of avapritinib and the end of follow-up, i.e. at least 24 months, until initiation of second-line treatment or until study discontinuation for any reason; whichever comes first (see Table 1). Survival is an exception and will be ascertained for all patients until study closure, which will

occur when the last patient enrolled has been followed for at least 24 months, or withdraws from the study for any reason.

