9.7.2. Statistical Methods

Descriptive analysis:

Demographic and other baseline characteristics collected before or at the time of the first avapritinib dose will be summarised for the SP. Continuous variables will be described (distribution) by their mean, standard deviation, median, extreme values (minimum and maximum) and the number of missing data. Categorical variables will be described using

frequency counts and percentages. Time-to-event data will be summarized by Kaplan-Meier (KM) estimates.

Analysis of the primary endpoint:

The primary endpoint for the study will be to describe AEs during the study period for the SP. Analyses will be conducted for the SP overall and stratified by treatment setting at the first dose of avapritinib and 300 mg dose, Eastern Cooperative Oncology Group (ECOG) performance status and country; feasibility requirements will be described in the SAP.

The study period for the safety analyses is defined as the time from the first dose of avapritinib to the end of follow-up, i.e. at least 24 months, until study discontinuation for any reason, or 30 days after the last dose of avapritinib; whichever comes first.

The following analyses will be performed:

- Number and proportions of patients experiencing an AE during the study period (i.e., from the first dose of avapritinib until the end of follow-up): by SOC (System Organ Class) and PT (Preferred Term) (MedDRA classification), severity, seriousness and relationship to avapritinib, including the description of types, severity and rates of AEs leading to discontinuation or decreased dosing of avapritinib.
- Number and proportions of patients with dose reductions or interruptions, or discontinuing avapritinib treatment due to an AE during the study period: overall and by comorbidity, including the description of types, severity and rates of AEs leading to discontinuation or decreased dosing of avapritinib.
- Incidence rate of patients experiencing an AE, overall and by SOC and PT terms
 - Defined as the number of patients with at least one (specific) AE during follow-up divided by the sum of person-months at risk in the study.
 - The sum of person-months at risk in the study when calculating the overall incidence is defined as the duration of follow-up for patients without AEs plus the duration of follow-up until the date of the first AE for patients with an AE.

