 - The sum of person-months at risk in the study when calculating the incidence for specific AEs is defined as the duration of follow-up for patients without the specific AE plus the duration of follow-up from baseline until the date of the first specific AE for patients with a specific AE, i.e. patients who experience another AE earlier in time will not be censored

Specific safety concerns that will be reported, include but are not limited to:

- Intracranial bleeding (e.g. cerebral haematoma, cerebral haemorrhage, haemorrhage intracranial, subdural haematoma)
- Cognitive effects (e.g. agitation, amnesia, cognitive disorder, confusional state, delirium, dementia, disorientation, encephalopathy, hallucination, memory impairment, mental impairment, mental status changes, mood altered, personality change, psychotic disorder, somnolence, speech disorder)
- Drug-drug interactions with moderate or strong CYP3A4 inhibitors or inducers

- Cardiac toxicity (e.g. electrocardiogram QT interval abnormal, electrocardiogram QT prolonged long QT syndrome, long QT syndrome congenital, torsade de pointes, ventricular tachycardia, cardiac arrest, cardiac death, cardiac fibrillation, cardio-respiratory arrest, electrocardiogram repolarisation abnormality, electrocardiogram U wave inversion, electrocardiogram u wave present, electrocardiogram U-wave abnormality, loss of consciousness, multiple organ dysfunction syndrome, subacute kidney injury, sudden cardiac death, sudden death, syncope, ventricular arrhythmia, ventricular fibrillation, ventricular flutter, and ventricular tachyarrhythmia)
- Embryofoetal toxicity
- Any off-label use in patients with severe hepatic impairment (Child-Pugh class C, i.e. ≥ 10 points, Annex 3)
- Drug-drug interactions with CYP3A4 substrates

Analysis of the secondary endpoints:

Secondary endpoints will be described using the SP. Analyses will be conducted for the SP overall and avapritinib dose 300 mg, and may be stratified by treatment setting at the first dose of avapritinib (i.e. study BLU-285-1101, CUP/EAP, and routine care), Eastern Cooperative Oncology Group (ECOG) performance status and by country if feasible; feasibility requirements will be described in the SAP.

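### Patients already on avapritinib may enrol without AE records from the first dose, yet their AE person-time is counted from the first dose, so primary AE estimates are biased downwards wherever early records are missing.

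*Protocol*

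**What the plan says.** Section 9.1 plans three groups: patients about to start avapritinib, patients already on it, and patients who have stopped it. The rules on earlier data differ between them.

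- **Eligibility (9.2.1).** "For patients who received avapritinib treatment and discontinued prior to enrolment in this study, their retrospective data must be available". No matching criterion covers patients still on treatment. The commitment in 9.3 to good-quality retrospective data also names only patients who discontinued.
- **Collection (9.1).** For anyone treated before enrolment, "retrospective data may also be collected (if data are available").
- **Collection (9.4, and likewise the Abstract).** "retrospective data will also be collected (if available").

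The analysis rules in 9.7.2 do not depend on whether early records exist.

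- **Safety period.** "The study period for the safety analyses is defined as the time from the first dose of avapritinib to the end of follow-up".
- **Person-months for a specific AE.** For patients with the event, "the duration of follow-up from baseline until the date of the first specific AE for patients with a specific AE"; for patients without it, the whole duration of follow-up. Footnote a of Table 1 ends the baseline period at the first avapritinib dose, so baseline is not enrolment.

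On timing, Section 7.1 reports for cognitive effects, one of the two AESIs, that "the probability of experiencing a cognitive effect increased over the first 7 to 8 months of treatment and then reached a plateau".

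**The concern.** A patient can be enrolled at, say, month 12 of treatment with no usable AE record for those 12 months. Under 9.7.2 the 12 months still count as time at risk, although no AE could have been recorded in them. An AE that began and ended in that window is also missing from the numerator of both the proportion and the rate.

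This touches the primary endpoint. The undocumented stretch is by construction the earliest part of treatment, which is when the protocol says cognitive effects accumulate. Section 9.9.1 plans to compare the AE rates found here with pooled rates from BLU-285-1101 and BLU-285-1303. Under-recording would make that comparison look favourable for a reason unrelated to safety, in a study that answers a Specific Obligation of the conditional authorisation.

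**Working it through.** **1. Direction.** Compare a previously treated patient with full records and the same patient without early ones. Losing early records can only remove a first event or move the first recorded event later. The numerator therefore stays the same or falls. The person-months, counted from the first dose to the first recorded event or the end of follow-up, stay the same or rise. Proportion and rate can only go down.

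**2. Inputs.**
- From the protocol: at least 50 patients (9.5); cognitive effects in 182/550 = 33% of the pooled patients and 46% in BLU-285-1101 (7.1); rise over the first 7 to 8 months, then a plateau (7.1); 24 months of prospective collection (9.4).
- Assumed, because the protocol does not give them: m, the number of patients already past month 8 at enrolment without early records (8 or 17 of 50); u, their undocumented months (12). Early events are taken as not recoverable.

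The protocol has no figure of its own to reproduce here. The calculation in 9.5 concerns ORR and plays no part.

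**3. Proportion with a cognitive effect.** If all such events fall before month 8, the observed proportion is p × (1 − m/50).

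| p | m | Events lost (m × p) | Observed |
|---|---|---|---|
| 33% | 8 | 2.6 | (16.5 − 2.6)/50 = 28% |
| 33% | 17 | 5.6 | (16.5 − 5.6)/50 = 22% |
| 46% | 8 | 3.7 | (23 − 3.7)/50 = 39% |
| 46% | 17 | 7.8 | (23 − 7.8)/50 = 30% |

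The event-free person-months added are 8 × 12 = 96 to 17 × 12 = 204.

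**4. Rate of an AE with constant hazard λ per month.** Mean documented time at risk is T = (1 − exp(−24λ))/λ. With f the share of patients without early records, the ratio of estimated to true rate is T/(T + f·u). For f = 8/50 = 0.16 and u = 12, f·u = 1.92:

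- λ = 0.01: 21.34/(21.34 + 1.92) = 0.92
- λ = 0.03: 17.11/(17.11 + 1.92) = 0.90
- λ = 0.05: 13.98/(13.98 + 1.92) = 0.88

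Over f from 20% to 60%, u from 6 to 24 months and the same hazards, the ratio runs from 0.95 to 0.49. Starting time at risk at the first documented month restores it to 1.00.

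**5. Rate of cognitive effects.** Spread the 33% evenly over months 0 to 8 (mean event time 4 months), with f = 0.16, u = 12 and 24 prospective months. Person-months are per enrolled patient.

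- A patient documented from the start contributes on average 0.33 × 4 + 0.67 × 24 = 17.40.
- Full records for all: 0.84 × 17.40 + 0.16 × (0.33 × 4 + 0.67 × 36) = 18.69, so the rate is 0.33/18.69 = 1.77 per 100 person-months.
- Gap counted as event-free: events 0.84 × 0.33 = 0.277, person-months 0.84 × 17.40 + 0.16 × 36 = 20.38, rate 1.36, ratio 0.77.
- Delayed entry: person-months 0.84 × 17.40 + 0.16 × 24 = 18.46, rate 1.50, ratio 0.85.
- Only patients documented from the first dose: proportion 33%, rate 0.33/17.40 = 1.90. This rate exceeds 1.77 only because these patients have fewer months after the plateau, not because events differ.

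Delayed entry thus corrects the denominator but does not recover the missed early events.

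**The case against.** The strongest reply is that the protocol, read whole, intends to collect these data. Sections 9.3, 9.4, 9.6 and the Abstract all provide for extracting earlier data when available, and the safety variables in 9.3 cover AEs that have already occurred. That stands: a reader might infer that collection is optional for continuing patients, but the single *may* in 9.1 is outnumbered. What remains is that each of these statements depends on availability, and none says what happens to the person-time when the data are not available.

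Second, 9.7 and 9.9.2 acknowledge poorer retrospective data and assign missing-data rules and sensitivity analyses to the SAP, which is not at hand. A reader might infer that the main estimate is certain to be wrong; that cannot be concluded. But eligibility, time origin and the person-month formula are set in the protocol, and an SAP cannot recover events that were never recorded. Enrolling more new patients, as 9.9.2 allows if feasible, dilutes the problem without removing the affected person-time. Including discontinued patients (9.9.1) addresses survivor bias, not this.

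Third, the asymmetry has a reason. For discontinued patients the past record is the only treatment-period record, whereas continuing patients also bring 24 prospective months. In an ultra-rare disease, admitting them despite imperfect early records is a defensible trade-off. This stands, and it argues against imposing a strict entry criterion as the only remedy.

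Fourth, the number of patients affected is assumed, and a cognitive effect that persists to enrolment could still be recorded. Both points stand; the figures above are illustrations and lean towards a larger loss.

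**Conclusion.** The concern holds for the primary AE proportions and incidence rates. Wherever a continuing patient lacks early AE records, the rules as written bias these estimates downwards, most for cognitive effects.

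The size cannot be fixed from the documents. It is nil with complete records. With 8 of 50 patients lacking early records, all past month 8 and with no early event recoverable, 33% becomes about 28%. With 12 undocumented months each, a constant-hazard AE rate is understated by about 8% to 12%, and the cognitive-effect rate by about 23%.

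A reader might infer that every endpoint is affected in the same way. The definitions in 9.7.2 do not support that:

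- **PFS and ORR** are affected in part: an early progression or response may be undocumented, or dated late.
- **DoR** runs from the first documented response, not the first dose.
- **DoT** needs only the first and last dose dates.
- **OS** is not affected by this mechanism, since a patient enrolled alive is known to have survived until then. Left truncation is a separate matter that complete AE records would not cure.

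**What to change.** 1. **Sections 9.1 and 9.3.** Change *may* to *will* in 9.1, in line with 9.4 and the Abstract, and state that AE records from the first dose are to be obtained for every patient treated before enrolment, whether treatment is ongoing or discontinued.
2. **Section 9.7.2, person-time.** State that AE person-time covers only periods for which AE records exist, with delayed entry at the first documented date.
3. **Section 9.7.2, main presentation.** Because delayed entry does not restore missed early events, give the main AE proportions and the cognitive-effect rate for patients documented from the first dose. Report patients with an early gap separately, with their number and undocumented months.

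Making records from the first dose an entry condition for continuing patients is an option for the sponsor to weigh against recruitment; it prevents the gap but could exclude patients in an ultra-rare population.

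The cost is a few sentences, slightly less person-time and a smaller denominator for some AE proportions. If sites hold complete records, nothing is lost.
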